Cover Page for Protocol

NCT04895293

Title: Evaluation of RBM-007 in subjects with treatment naïve exudative age-related macular

degeneration (TEMPURA Study)

Study: RKM-011

Date: 11 April 2021

Statistical plans contained within protocol

Clinical Study Protocol RKM-011

Evaluation of RBM-007 in subjects with treatment naïve exudative agerelated macular degeneration

Protocol Number: RKM-011

Investigational Product: RBM-007 Injectable Solution

Indication: Treatment of exudative age-related macular

degeneration

Phase: Phase 2

Sponsor: [name]., P.C.

N

Phone

Medical Monitor [name]., P.C.

Protocol Date: 11 April 2021

Protocol Version: Initial Replaces: N/A/

Contact Information and Protocol Authorization

Clinical Study Protocol RKM-011 Phase 2

Protocol Title: Evaluation of RBM-007 in subjects with treatment naïvage-related macular degeneration						
Protocol Number:	RKM-011					
amendments), Interna	conducted in compliance with the clinical study protocol (and ational Conference on Harmonisation (ICH) guidelines for current ce (GCP) and applicable regulatory requirements.					
Sponsor Signatory:						
	[name]., P.C.					
	Date:					

TABLE OF CONTENTS

1 PR	OTOCOL SUMMARY	4
2 BA	CKGROUND AND CLINICAL RATIONALE	6
3 ST	UDY OBJECTIVES	6
4 ST	UDY DESIGN	6
	UDY POPULATION AND ENTRY CRITERIA	
	Number of Subjects:	
	Inclusion Criteria:	
5.3	Exclusion Criteria:	. 7
	Permissible Medications/Treatments:	
5.5	Prohibited Medications/Treatments:	8
6 ES	CAPE CRITERIA/ MEDICATIONS	9
	Escape Criteria:	
6.2]	Escape Medications:	9
7 ST	UDY TREATMENT	9
	Randomization:	
	Administration	
7.3	Investigational drug: RBM-007:	10
8 SA	FETY MEASURES1	0
9 AD	VERSE EVENTS1	0
10 ME	THOD OF ANALYSIS1	1
10.1	General Data Summaries	
10.2	Efficacy evaluation	1
11 ST	UDY VISIT SCHEDULE AND PROCEDURES1	11
12 AD	MINISTRATIVE ITEMS1	13
13 RE	FERENCES	12
13 KE	PEREICES	. J
APPEND	IX A: INJECTION PROCEDURE FOR ALL SUBJECTS	15
List of t	ables	
Tarif 1	· SCHEDIU F OF VISITS AND EVENTS	17

1 Protocol Summary

Study Compound: RBM-007

Phase: 2

Study Objective: To determine safety and efficacy of intravitreal injections of RBM-007 in subjects with treatment naïve exudative AMD in the study eye.

Clinical Hypothesis: RBM-007, as used in previous trials of neovascular AMD, has shown an improvement in vision as well as an improvement in subretinal fibrosis in a cohort of subjects with chronic wet AMD. The mechanism of action of RBM-007 is distinct from that of Anti-VEGF treatments. RBM-007 has a powerful fibroblast growth factor-2 inhibition which serves to reduce both VEGF expression as well as inhibit FGF based neovascular response and fibroblast-proliferation. Having both mechanisms of action active early in the disease process will reduce the development of fibrosis in naïve wet-AMD subjects and potentially provide an improved and sustained visual function and favorable anatomic change.

Structure: Single site, open label study

Duration: 4 months

Study Treatment group:

• RBM-007 treatment at baseline, month 1 and month 2. Safety evaluations at week 2, months 3 and 4.

Randomization: all study subjects will receive study drug and those non-responsive to study drug will be treated with rescue anti-VEGF drug, in addition to continuing RBM-007

Visit Schedule:

There will be 6 scheduled visits during the study. These include baseline (Day 0), week 2, and months 1, 2,3, 4/exit.

Primary endpoint one month after the last RBM-007 injection (month 3)

Study Population Characteristics

Number of subjects: Up to 5 subjects will be enrolled

Condition/Disease: Naïve exudative Age-Related Macular Degeneration with associated visual loss.

Key Inclusion Criteria:

- Aged 50 or older, diagnosed with exudative AMD.
- BCVA 5-73, inclusive, in study eye
- Presence of choroidal neovascularization (CNV) secondary to AMD, in study eye

Key Exclusion Criteria:

- History of major ophthalmic surgery in the past 3 months, and any ophthalmic surgery in study eye in the last 30 days
- History of significant ocular disease other than exudative AMD that many confound results
- Hypersensitivity to components of study medication

Response Measures

Efficacy:

- Change in BCVA from baseline to month 3
- Change in intraretinal and subretinal fluid from baseline to month 3, as measured by CST on Heidelberg OCT
- Change in OCT-angiography in study eye from baseline to month 3
- Number of subjects escaping to standard of care
- Change in measured area of intraretinal/subretinal fibrosis

Safety: adverse events, BCVA, complete ophthalmic examination, physical examination and vital signs.

All adverse events and serious adverse events will be continually assessed throughout the study. The investigator will assess safety throughout the study to determine appropriateness of continuing dosing and enrollment.

General Statistical methods and Types of Analyses:

The primary efficacy endpoint is:

• Change in edema from baseline to month 3 (one month after the last injection) as measured by CST on Heidelberg OCT

Secondary endpoints include the following:

- Change in BCVA from baseline to month 3
- Change in intraretinal and subretinal edema from baseline to month 3
- CNV lesions components: subretinal hyper-reflective material (SRHM), PED thickness
- Number of subjects escaping to standard of care treatment
- Change in size of OCT-angiography leakage from baseline to month 3

2 Background and Clinical Rationale

Age-related macular degeneration (AMD) is the leading cause of severe vision loss in people over the age of 65 in the United States.¹ The majority of severe vision loss due to advanced AMD is related to the onset of choroidal neovascularization (CNV).^{2,3} Neovascular AMD is characterized by the growth of choroidal vessels into the subretinal space. These vessels have a tendency to leak fluid and blood, causing retinal edema and central vision loss.

The CATT study data demonstrates that it is difficult to achieve anatomic flattening of the macula in patients with neovascular AMD.⁴ After one year of required monthly treatment in both the bevacizumab and ranibizumab groups, approximately 50% of subjects continued to have intraretinal and/or subretinal fluid on optical coherence tomography.⁴ When fluid is present in these structures, retreatment is generally necessary to stabilize vision – and subjects with persistent fluid generally have poorer visual gain. RBM-007 has shown, in a previous clinical trial (see attached SUSHI Study CSR) evidence of bioactivity, reducing macular edema associated with choroidal neovascularization in wet AMD. Additionally, the mechanism of action of RBM-007 is more expansive than that of Anti-VEGF treatment alone as RBM-007, a novel oligonucleotide-based aptamer, has potent anti-FGF2 activity, which leads to reduced VEGF expression.^{5,6} In the rat and mouse models of laser-induced choroidal neovascularization, RBM-007 showed activity after intravitreal injection at doses as low as 5 μg/eye⁷. In the laser-induced choroidal neovascularization fibrosis model in rats, it showed activity after intravitreal injection at doses as low as 15 μg/eye⁷ (see Ribomic Investigator Brochure for RBM-007, 2020).

3 Study Objectives

To determine safety and efficacy of intravitreal injections of RBM-007 in subjects with naïve exudative AMD.

4 Study Design

This study is a single-center, open label, 4-month study, designed to evaluate the safety and treatment efficacy of RBM-007 in patients with intraretinal or subretinal edema due to previously untreated neovascular AMD. Up to 5 subjects will be randomized to receive study medication. Study treatment will be administered by intravitreal injections.

There will be 5 scheduled visits during the study. See table 1.

5 Study Population and Entry Criteria

5.1 Number of Subjects:

5

Study Population Characteristics: If both eyes meet all of the inclusion/exclusion criteria the eye with the worse BCVA at baseline will be selected as the study eye. If both eyes meet all of the

inclusion/exclusion criteria and BCVA values are identical for both eyes, the right eye will be selected as the study eye.

5.2 Inclusion Criteria:

• General Inclusion Criteria:

- 1. Male or female patients, 50 years of age or older at baseline
- 2. Patient has completed/signed an informed consent prior to any study-related procedures and is able to follow study instructions and likely to complete all required visits.

• Ocular Inclusion Criteria:

- 3. BCVA 5 73 ETDRS letters (20/800-20/40 Snellen equivalent), inclusive, in study eye
- 4. Presence of choroidal neovascularization secondary to AMD
- 5. Clear ocular media and adequate pupil dilation to permit good quality photographic imaging.

5.3 Exclusion Criteria:

• General Exclusion Criteria:

- 1. Females who are pregnant, nursing, planning a pregnancy or who are of childbearing potential not using a reliable method of contraception.
- 2. History or current evidence of hypersensitivity to any components of the study medication or fluorescein, as assessed by the investigator.
- 3. Participation in any investigational drug or device study within 30 days prior to baseline
- 4. History or current evidence of a medical condition that may, in the opinion of the investigator, preclude the safe administration of study medication or affect the results of the study.

• Ocular Exclusion Criteria:

- 5. Active ocular or periocular infections, malignancy
- 6. Aphakia
- 7. History of pars plana vitrectomy in the study eye
- 8. History of major ophthalmic surgery in the past 3 months in the study eye, or minor surgery in the past 30 days
- 9. History of significant ocular disease other than exudative AMD that may confound results
- 10. Uncontrolled glaucoma (defined as intraocular pressure >21mm Hg despite treatment with ocular hypotensive medications at baseline).

5.4 Permissible Medications/Treatments:

• Therapy considered necessary for the patient's welfare may be given at the discretion of the investigator. Therapies for the non-study eye are permissible at any time.

5.5 Prohibited Medications/Treatments:

Systemic anti-VEGF medications, or systemic anti-fibroblast growth factor mediations.

Confidential

6 Escape Criteria/ Medications

6.1 Escape Criteria:

- Subjects with a 10 letter decrease at two consecutive visits or a 15 letter decrease at any visit may be escaped to standard of care.
- Central retinal thickness increase by 50 µm or more associated with at least a 5-letter decrease may be escaped to standard of care
- Presence of new hemorrhage, worsening hemorrhage, new extra foveal fluid, or at the discretion of the investigator.
- **Note:** Subjects that escape to standard of care will continue to be followed for safety through the four-month study period.

6.2 Escape Medications:

• Subjects that escape to standard of care may receive treatment with medications at the investigator's discretion, which in most cases would be an intravitreal Anti-VEGF drug (Eylea, or another drug as determined by the investigator).

7 Study Treatment

RBM-007 injectable solutions (20 mg/mL) are filled (0.5 mL fill) in 2-mL Type 1 Glass (borosilicate) clear vials, capped with 13 mm Gray Butyl stoppers with B2-40 coating (on top) and FluroTec coating

(on bottom), and sealed. Three single use vials will be placed in a carton, and the labeling will include protocol number, kit number, drug concentration and storage conditions. RBM-007 injectable solutions will be provided by RIBOMIC/Representative and will be stored in an appropriate secure area at the investigational site. RBM-007 vials should be protected from light, stored upright, and kept at -20°C.

7.1 Randomization:

Not applicable for this open-label, single-treatment study.

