10.1 General Data Summaries

Continuous variables will be summarized with means and standard deviations and medians with min and max values and categorical variables with frequencies and percentages. Standard parameters and statistical tests will be performed to evaluate for the primary and secondary end points. Specifically, mean change in the CST, manual determination for the presence of subretinal fluid and intraretinal fluid at month three (and at other time points), change in BCVA between baseline and month three, and the number of anti-VEGF injections needed will be measured. Based on the results of these tests, additional testing, as outlined below, may be performed.

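### Does measuring retinal fluid by CST in one place and by manual reading in another leave the fluid endpoint open?

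*Combined protocol and SAP*

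**What the plan says.** Four statements bear on the point.

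- Section 1, Response Measures, lists as an efficacy measure "Change in intraretinal and subretinal fluid from baseline to month 3, as measured by CST on Heidelberg OCT". The list does not mark any item as primary or secondary.
- Section 1, under general statistical methods, gives the primary efficacy endpoint as "Change in edema from baseline to month 3 (one month after the last injection) as measured by CST on Heidelberg OCT".
- The secondary endpoints that follow include "Change in intraretinal and subretinal edema from baseline to month 3", with no instrument or metric named.
- Section 10.1 says that "mean change in the CST" will be measured and, as a separate item, "manual determination for the presence of subretinal fluid and intraretinal fluid at month three (and at other time points".

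Two other places give context. Section 6.1 lists "Central retinal thickness increase by 50" µm or more (with a loss of letters) and, in another bullet, "Presence of new hemorrhage, worsening hemorrhage, new extra foveal fluid" among the escape criteria. Section 2 cites an earlier anti-VEGF trial in which, after a year of monthly treatment, "approximately 50% of subjects continued to have intraretinal and/or subretinal fluid on optical coherence tomography".

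CST is not spelled out. It is read here as a central thickness measurement.

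**The concern.** Thickness and fluid are different things. A single thickness value per eye cannot give separate answers for intraretinal and subretinal fluid. It can also fall while some fluid remains, or while new fluid appears away from the centre. Section 6.1 treats central thickening and new extrafoveal fluid as separate signs of worsening, so the protocol itself recognises the difference.

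If the CST wording in Response Measures supplied the measure missing from the fluid secondary, that secondary would equal the primary in every eye. A fall in mean CST could then be reported twice, once as less edema and once as less fluid, even if no eye had cleared. The rationale in Section 2 rests on persistence of fluid, so this would weaken the conclusion that matters most to it. In an open-label study with the definition unsettled, one might also fear that the more favourable version would be chosen once the scans had been read.

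**Working it through.** The plan states no sample-size, power or alpha figure on this point, so there is nothing to reproduce. The check sets the passages side by side and then looks at the arithmetic that might be offered for the size of the problem.

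**Step 1: what the Response Measures line is.** Matching the two lists in Section 1:

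| Response Measures item | Counterpart in the endpoint list |
|---|---|
| BCVA change | Secondary |
| Fluid change by CST | Primary (edema by CST; same interval, same device) |
| OCT-angiography change | Secondary |
| Number escaping | Secondary |
| Fibrosis area | None |

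Only one line in Response Measures mentions CST. If it is not the primary endpoint, the primary is missing from the efficacy list altogether. The natural reading is that it is the primary, with the word fluid in place of edema.

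**Step 2: whether a secondary duplicates the primary.** There are 5 secondary bullets. One of them would equal the primary only if the CST wording were carried from Response Measures into the fluid secondary. The secondary's own text does not do this. Section 10.1 offers a measure that fits it at least as well: manual presence of each fluid type.

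**Step 3: what an analyst would produce.**

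| Reading | CST change reported? | Manual presence of each fluid reported? |
|---|---|---|
| Response Measures line is the primary | Yes (primary; Section 10.1) | Yes (Section 10.1) |
| Response Measures line defines the fluid secondary | Yes (primary; Section 10.1) | Yes (Section 10.1) |

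The readings differ only in which result carries the label of fluid secondary. Table 1 schedules Heidelberg OCT at all 6 visits, baseline included, and Section 10.1 covers month 3 and other time points. A comparison of presence between baseline and month 3 can therefore be made from planned data.

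**Step 4: how often the two measures might part.** Let p be the chance that fluid persists at month 3 and q the chance that CST falls in such an eye. For n = 5 independent subjects, r = p × q, the expected number is 5r, and the chance of at least one is 1 − (1 − r)^5.

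| Case | p | q | r | 5r | Chance of at least one |
|---|---|---|---|---|---|
| Low | 0.30 | 0.50 | 0.15 | 0.75 | 1 − 0.85^5 = 0.556 |
| Central | 0.50 | 0.75 | 0.375 | 1.875 | 1 − 0.625^5 = 0.905 |
| High | 0.70 | 1.00 | 0.70 | 3.5 | 1 − 0.30^5 = 0.998 |

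The arithmetic is right but does not show a conflict. It counts eyes that are thinner and still have some fluid, and those two findings are compatible. Truly opposite results need new fluid together with a stable or falling CST, and the documents give no basis for estimating how often that happens. As to the inputs, q has no source in the documents, and the central p comes from a year of monthly anti-VEGF treatment, not three RBM-007 injections.

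**The case for a change.** The strongest case for a change is that the wording is inconsistent on any reading. Even if the Response Measures line is the primary, it still calls a thickness change a fluid change, and the fluid secondary still has no stated measure. In a descriptive study the endpoint definition decides what is reported, and with 5 subjects one eye moves a presence rate by 1/5 = 20 percentage points. The plan also does not say how a presence reading becomes a change from baseline. Clearer wording would cost almost nothing.

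The observation about wording stands. The consequences do not. Both measures are written into Section 10.1, so neither depends on a choice made after the scans are read; a reader who sees a lower CST will also see whether fluid remains. The 20-point step comes from having 5 subjects and would be the same under any wording. An eye with new extrafoveal fluid and a stable CST is visible in a second way too: that finding is among the escape criteria, and the number escaping is its own secondary. Escape is optional, so this cover is only partial.

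More elaborate remedies do not follow either. Visit-masked reading of the whole scan may need another reader at a single open-label site. Shift tables are a matter of presentation. A pure yes/no measure would also score an eye that lost most of its fluid as unchanged, so CST is a useful companion to it.

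**Conclusion.** No change to the plan follows. The labels are loose: Response Measures describes the CST change as a fluid change, and one secondary names no measure. Section 10.1 fills the gap by planning the CST change and the manual presence of each fluid type as separate results. A sensible analyst would report the first as the primary and the second under the fluid secondary.

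The effect on results is nil: the same CST values and the same fluid readings are produced under either reading. No error rate is at stake, because the plan sets no alpha or power and the efficacy evaluation in Section 10.2 is descriptive, although Section 10.1 mentions unspecified tests. At most, the label on one of 5 secondaries in a study of up to 5 subjects is affected.

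The conclusion rests on two assumptions: that CST is a central thickness measurement, and that the manual readings promised in Section 10.1 are reported alongside the CST change.

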10.2 Efficacy evaluation

Descriptive statistics will be performed on all subjects with special care taken to carefully analyze the change in OCT-A, OCT determined macular thickness, visual acuity (BCVA), fundus autofluorescence and fluorescein angiography. All subjects randomized (ITT population) will be included in the analysis, and subjects will be grouped according to the number of study treatments received (if less than 3). Safety parameters will be evaluated in the patient population.

11 Study Visit Schedule and Procedures

Please see Table 1 for a schematic of the schedule of visits and procedures. The visit schedule includes 5 scheduled visits: baseline, month 1, 2, 3, and 4.

Baseline visit:

- obtain informed consent and authorization
- collect demographic information and medical and ophthalmic history
- collect information about concomitant medication and procedures
- physical examination
- vital signs (blood pressure and pulse rate)
- Pregnancy Test (if indicated)

Perform the following procedures in both eyes:

• standard BCVA, using ETDRS method following refraction

- complete ophthalmic examination: slit-lamp biomicroscopy, indirect ophthalmoscopy and IOP
- Heidelberg OCT imaging
- Angiovue OCT-A imaging
- dilated fundus photography (Heidelberg)
- fluorescein angiography (Heidelberg)
- autofluorescence fundus photography (Heidelberg)
- confirm eligibility
- perform intravitreal injection in study eye (treat fellow eye as standard of care, as indicated)
- query for adverse evets

Week 2 Safety Assessment Visit

- query for adverse events
- query for medication changes and medical procedures
- if rescue criteria met, treat with anti-VEGF at this visit.

Perform the following procedures in both eyes:

- standard BCVA, using ETDRS method following refraction
- complete ophthalmic examination: slit-lamp biomicroscopy, indirect ophthalmoscopy and IOP
- Heidelberg OCT imaging
- Angiovue OCT-A imaging

Month 1, and 2 visits

- query for adverse events
- query for medication changes and medical procedures
- if rescue criteria met, treat with RBM-007 then, standard of care anti-VEGF at that visit. An anterior chamber paracentesis will be performed at the visit as well for intraocular pressure control. Treatment with RBM-007 may be withheld per investigator discretion.

Perform the following procedures in both eyes:

- standard BCVA, using ETDRS method following refraction

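### Must the OCT-angiography secondary endpoint be tied to one quantity and unit before any images are read?

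*Combined protocol and SAP*

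**What the plan says.** The endpoint appears in three forms.

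- Section 1, secondary endpoints: "Change in size of OCT-angiography leakage from baseline to month 3".
- Section 1, Response Measures: "Change in OCT-angiography in study eye from baseline to month 3".
- Section 10.2, within a list to be summarised descriptively: "change in OCT-A, OCT determined macular thickness, visual acuity (BCVA), fundus autofluorescence and fluorescein angiography".

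On analysis, Section 10.1 states: "Standard parameters and statistical tests will be performed to evaluate for the primary and secondary end points". It then names specific variables: CST, presence of subretinal and intraretinal fluid, BCVA, and the number of anti-VEGF injections. It closes with "Based on the results of these tests, additional testing, as outlined below, may be performed". Section 10.2 follows and plans descriptive statistics.

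Table 1 schedules OCT-angiography at all six visits, and fluorescein angiography at baseline and Month 4 only. The cover page says that the statistical plans are contained in the protocol, so no separate SAP settles the point.

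**The concern.** Two readings of the endpoint can be drawn from the protocol's own words.

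- **Fluid.** Section 2 says of the new vessels: "These vessels have a tendency to leak fluid and blood, causing retinal edema and central vision loss". On that usage, leakage is what leaves the vessels, and its size is an amount or area of fluid.
- **Vessels.** The Response Measures list drops the word leakage, and the clinical hypothesis is that the drug will "inhibit FGF based neovascular response and fibroblast-proliferation". On that usage, the endpoint is the size of the neovascular lesion or vessel network.

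A fall in fluid with unchanged vessels would count as improvement on the first reading and as no change on the second. The study is open label at a single site and no masked reader is mentioned, so the quantity could in principle be settled after the outcomes are known. If the endpoint were formally tested, and the result could trigger further testing, that freedom would raise the chance of a spurious positive finding.

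**Working it through.** The plan gives no alpha, power, effect size or SD, so it has no figure to reproduce. The check is mainly a reading of the text, followed by the arithmetic that might be held against the plan.

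**1. What is fixed and what is open.**

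| Place | Modality | Eye | Time frame | Quantity and unit |
|---|---|---|---|---|
| Section 1, secondary endpoints | OCT-angiography | not repeated | baseline to Month 3 | size of leakage, no unit |
| Section 1, Response Measures | OCT-angiography | study eye | baseline to Month 3 | not named |
| Section 10.2 | OCT-A | not repeated | not repeated | not named |

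Only the last column is open. The images will exist at both time points.

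**2. Is a test of this endpoint planned?** Only the general sentence in Section 10.1 implies one. The next sentence narrows it to four items, none of them OCT-angiography. The additional testing is said to be outlined below, but what follows in Section 10.2 is descriptive. A formal OCT-angiography test is therefore an inference from one general sentence, and the text that names the endpoint points the other way.

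**3. Which reading fits the document?** Section 1 lists 1 primary and 5 secondary endpoints, 6 in all. Two already measure fluid: edema by CST (primary) and "Change in intraretinal and subretinal edema from baseline to month 3" (secondary).

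- Fluid reading: 2 + 1 = 3 of 6 endpoints measure fluid and 0 are angiographic.
- Vessel reading: 2 of 6 measure fluid and 1 is angiographic.

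The fluid reading makes the endpoint a third measure of the same thing. It also fits poorly with the lists: Response Measures assigns fluid to CST on structural OCT and gives OCT-angiography its own line, and Section 10.2 separates OCT-A from OCT macular thickness. The fluid reading rests on a background sentence about disease biology, not on one about what is read from the scan. Leakage on fluorescein angiography cannot be meant, because none is scheduled at Month 3.

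**4. The cost of choosing between two readings.** Assume no true change, 5 subjects each equally likely to go up or down, and the better of two measures reported.

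- At least 4 of 5 improve on one measure: (5 + 1)/32 = 18.75%.
- The same on the better of two independent measures: 1 − (1 − 0.1875)² = 34.0%. At correlation 0.8 it is 27.7% (1,000,000 simulated studies).
- At least one of two independent tests significant at two-sided 5%: 1 − 0.95² = 9.75%. Simulated paired t-tests at n = 5 give 8.4% at correlation 0.8 and 6.9% at 0.95.
- Smallest two-sided exact sign or signed-rank p-value at n = 5: 2/32 = 0.0625.

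The arithmetic is correct, but it does not describe this protocol. No rule of 4 in 5 improving appears anywhere, and no t-test or alpha is named. With an exact sign or signed-rank test, no result could reach 5% on either measure, so at that level there would be nothing to inflate. The same figures would hold for any two measures in any study of 5 subjects.

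**5. Would fixing the quantity make the result firmer?** With n = 5, the 95% confidence interval for a mean change has half-width 2.776/√5 = 1.24 SD. A paired t-test at an assumed two-sided 5% needs a true mean change of about 1.68 SD for 80% power. The endpoint stays descriptive in practice, whichever quantity is named.

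**The case for a change.** The strongest opposing case is that the protocol is more exact elsewhere: it names CST on a given device, PED thickness and a measured area of fibrosis. Here it gives the size of a feature it never defines. Even a descriptive mean cannot be computed until someone names the quantity. With so few subjects, the choice of measure can strongly colour the impression given. The remedy would be a few words, with no added procedure.

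Part of this stands. There is no unit, leakage is a loose word, the three wordings differ, and Sections 10.1 and 10.2 do not agree on whether the secondary endpoints are tested or only described. Anyone tidying the text for other reasons could settle these points together.

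The step from loose wording to a flawed analysis does not stand. The two readings are an interpretation; the protocol does not offer them as alternatives, and its structure favours one of them. Naming a quantity and unit would not by itself remove discretion either, since the scan area, segmentation and reader would still be open.

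**Conclusion.** The description is incomplete, but no change to the plan is needed. This is a missing detail that analysts would most likely fill sensibly with a lesion or vessel measure, naming that measure when they report it. No stated rule or number in the protocol gives a wrong result because of it.

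The reach is 1 of 5 secondary endpoints, described rather than tested in the only analysis text that names it, in a single-arm study of up to 5 subjects. No decision in the protocol depends on it, and the primary endpoint is unaffected.

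This rests on two judgements: that Section 10.2 and the specific list in Section 10.1 govern over the general sentence on testing, and that the separate listing of OCT-angiography shows it was not meant as another fluid measure. If a formal OCT-angiography test were later presented as evidence of effect, the reader should ask when the quantity was chosen.
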